## ABBREVIATIONS

FHCRC	Fred Hutchison Cancer Research Center
UW	University of Washington
SoN	School of Nursing
SoM	School of Medicine
SCCA	Seattle Cancer Care Alliance
IRB	Institutional Review Board
CRF	Cardiorespiratory Fitness
QoL	Quality of Life
CVD	Cardiovascular disease
VO 2	Volume Oxygen
CPET	Cardiopulmonary Exercise Testing
MRI	Magnetic Resonance Imaging
AE	Aerobic Exercise OR Adverse Event
RE	Resistance Exercise
IMF	Intermuscular Fat
6MWT	Six Minute Walk Test
6MWD	Six Minute Walk Distance
DSM	Data & Safety Monitoring
SAE	Serious Adverse Event

## 1.0 INTRODUCTION

This document is a clinical research protocol. The described study will be conducted in compliance with the IRB approved protocol, associated Federal regulations, and all applicable IRB requirements. This study is being performed in order to examine the feasibility of administering an individually tailored exercise intervention among breast cancer survivors. Specifically, we will conduct a pilot study of a 2-arm exercise intervention among breast cancer survivors with reduced cardiorespiratory fitness.

## 2.0 BACKGROUND

### 2.1 Cardiorespiratory fitness decline in breast cancer survivors

**Cancer survivors experience substantial reductions in cardiorespiratory fitness.** Improved cancer treatment has led to 3.8 million breast cancer survivors in the U.S. today. However, this improvement is offset by an increase in cancer therapy-related morbidity and mortality. In particular, up to one-third of chemotherapy-treated breast cancer patients, particularly those receiving anthracycline chemotherapy, experience substantial reductions in cardiorespiratory fitness (CRF) – defined by functional limitations (e.g., becoming out of breath when walking across a room). Unfortunately, many of these women do not regain their fitness after treatment cessation. A recent study demonstrated that even treatment historically thought to be well-tolerated is associated with long-term marked impairment of cardiorespiratory fitness.

This substantial loss of fitness leads to a lower quality of life (QoL) and reduces a survivor's ability to maintain activities of daily living. Reduced cardiorespiratory fitness also increases the risk of late-occurring cardiovascular disease (CVD), and in cancer survivors strongly predicts CVD mortality. Thus, an increased burden of CVD in these patients adds another layer of complexity and challenges to this already vulnerable cohort. Overall reduced cardiorespiratory fitness is associated with a 3-fold increased risk of death.

**Cardiac and skeletal muscle composition affect CRF.** The factors that increase the risk of reduced cardiorespiratory fitness in chemotherapy-treated survivors are multifaceted and extend beyond cardiac-specific factors. Cardiorespiratory fitness is reflective of multiple organ systems, and as such is a useful metric to estimate total body health. Unfortunately, it is well-documented that cancer treatment can lead to dysfunction of many organ systems, including skeletal muscles and cardiac muscles. The changes to cardiac muscles and skeletal muscle composition – known as the cardiovascular-skeletal muscle axis – are known to play a critical role in cardiorespiratory fitness. A 2018 White Paper concluded that interventions to improve cardiorespiratory fitness in cancer survivors should focus on damage that occurred along this axis. Thus, interventions may need to incorporate aerobic and resistance training, depending on whether treatment-induced changes occurred to both the cardiovascular system and skeletal muscles.

### 2.2 Intervention

**Individualized interventions targeting CRF in breast cancer are needed.** Past research has demonstrated the need for individually-adaptive interventions to ameliorate CRF reductions in cancer

survivors. A meta-analysis showed significant heterogeneity in the effects of exercise interventions on fitness. While across the total cohort, exercise interventions led to significant improvements among cancer survivors, approximately one-third of participants receiving an aerobic exercise intervention saw no improvements and one-quarter continued to lose fitness, which suggests a need for examining avenues beyond aerobic training for improving CRF. This is particularly important for patients who demonstrated progressive fitness loss that continued to worsen even after completing exercise treatment.

There is a need to develop individually-tailored interventions, particularly for the subcohort that demonstrate reductions in cardiorespiratory post-cancer treatment. This is aligned with a recent American Heart Association position paper stating that research is needed to determine the types of exercise intervention that are effective at improving fitness in cancer survivors. As there is no proven strategy to improve fitness in breast cancer survivors, providers lack an evidence base to offer an 'exercise prescription' to patients, the lack of which contributes to lower physical activity in breast cancer survivors.

We can glean information on the contributors to reductions in cardiorespiratory fitness from the Fick equation which states that exercise capacity is a product of cardiac output and the  $\text{AVO}_2$  difference, a measure of oxygen differential between the arterial and venous system which reflects peripheral factors, including the ability of the skeletal muscle to oxygenate. Thus, non-cardiac factors, such as skeletal muscle dysfunction, could potentially contribute to reduced cardiorespiratory fitness in breast cancer survivors. This is supported by literature indicating in particular that increased intermuscular fat negatively impacts the skeletal muscle's ability to oxygenate as well as increased intermuscular fat was the predominant factor in breast cancer survivors with reduced cardiorespiratory function.

As it is yet unclear whether cancer survivors would benefit most from aerobic or strength training, this study will be the first step toward designing an intervention to test whether one exercise modality has superiority over another among cancer survivors. Thus, an adaptive intervention is an ideal design to determine which type of intervention is optimal. We propose to employ an intervention in which participants who are not responding to an exercise modality are re-assigned to a combined modality, thus tailoring the exercise intervention to respond to the needs of participants.

### **2.3 Experience and Preliminary Work**

Our interdisciplinary research team has previously implemented a lifestyle intervention in a pilot study of women at high risk of breast cancer, some of whom were breast cancer survivors, that involved a similar focus on exercise intervention and utilized a similar recruitment plan to identify and enroll participants. In addition, our research team has expertise in assessment of functional exercise capacity (e.g., 6-minute walk distance, cardiopulmonary exercise testing) and of body fat depots, particularly IMF and depots of abdominal adiposity using magnetic resonance imaging (MRI).

### **2.4 Risks/Benefits**

Anticipated risks. No serious risks are anticipated with this study. Cardiopulmonary exercise testing (CPET) may cause some fatigue and physical discomfort. Psychological discomfort, such as anxiety or apprehension, may arise for participants related to undergoing MRI and CPET. These are not seen as significant risks with levels of discomfort beyond those that they might experience during situations

outside of the study. Participants will be informed that they can stop participating in the study at any time.

Risks associated with the intervention are minimal, even for individuals with reduced cardiorespiratory fitness. However, adverse events may occur with exercise:

*Exercise training.* The major risks of participating in this monitored program include muscle fatigue, muscle soreness, and possible joint or skeletal injury. These risks are reduced by enrolling women without contraindications to exercise modifications, proper warm-up/cool down periods, conservative exercise prescriptions and progression, and monitoring by experienced staff (including exercise physiology specialists). If experienced, exercise-related injuries are expected to be of minimal discomfort and short duration and not significantly different than what someone might experience in everyday physical activities.

The study will maintain ongoing compliance with all University of Washington guidelines surrounding COVID-19 mitigation for in-person clinical research.

All adverse events, regardless of attribution to study procedures, will be collected and recorded. Subjects will be asked in an open-ended way about the presence of any adverse events. The PI will comply with all requirements of the IRB for the reporting of safety data and adverse/serious adverse events. For more information, see the study Data & Safety Monitoring (DSM; Appendix A)

Storing all data with only a code attached will help ensure confidentiality. However, there is a potential risk of breach of confidentiality related to collection of sensitive information and participant identifiers. Following procedures outlined in Section 9.0 will minimize possible breaches of confidentiality and obtaining informed consent will limit invasion of privacy.

**MRI risk management.** Participants in our study will not receive gadolinium-based contrast agents for the MRI scans.

**Anticipated direct benefits to participants.** Participants in the intervention group may benefit from a free, semi-supervised exercise program. All physiologic measures are performed and analyzed for research purposes only; we do not plan to share findings with participants.

**Individual participants' findings.** Generally, individual findings will not be shared with the participant. We do not anticipate the MRI will produce any timely, clinically actionable results. If a life-threatening condition is identified through the CPET, this result will be shared with the participant.

### **3.0 STUDY AIMS**

1. Determine the feasibility of an individually-adaptive exercise intervention among breast cancer survivors with reduced cardiorespiratory fitness through examination of recruitment rate, enrollment rate, loss to follow-up, intervention adherence, and relative dose intensity (ratio of total completed to total planned cumulative dose)

2. Examine the endpoint of (a) safety; and explore the endpoints of (b) cardiorespiratory fitness; (c) functional capacity; (d) physiologic changes; and (e) patient reported outcomes (PRO) in the intervention vs control arms.
3. Examine the endpoint of (a) safety; and explore the endpoints of (b) cardiorespiratory fitness; (c) functional capacity; (d) physiologic changes; and (e) patient reported outcomes (PRO) in the AE vs RE vs AE+RE intervention arms.

## 4.0 STUDY DESIGN

### 4.1 Description of Study

This is a pilot study of a 2-arm randomized trial with a 2:1 initial allocation to exercise intervention or waitlist control (see Appendix B for study schema). The intervention group will then be randomly assigned (1:1) to receive either a 12-week aerobic exercise (AE) intervention or a 12-week resistance exercise (RE) intervention.

At 12 weeks, the intervention group will be assessed for intervention response, defined as a  $\geq 5\%$  increase in 6-minute walk distance (6MWD) over baseline. Non-responders to either AE or RE will receive 12 weeks of combined AE+RE. Intervention responders will continue the exercise intervention in their current assignment, either AE or RE alone, for the additional 12 weeks.

This study will employ a waitlist control. After 24 weeks, the waitlist control group will receive a digital copy of sessions provided to the intervention arm. The control and intervention arms' schedule of evaluations will be identical across all 24 weeks of the trial.

### 4.2 Endpoints

#### 4.2.1 Primary Endpoint

Intervention Feasibility: Intervention feasibility will be determined with all-cause intervention discontinuation rate, which is the proportion of all intervention participants who permanently stop the intervention prior to Week 24 for any reason.

#### 4.2.2 Secondary Endpoint

The secondary outcomes include:

##### *Intervention Safety*

Safety: Intervention safety will be determined by reviewing and quantifying the number of adverse events (mild, moderate, or severe), serious adverse events, and by reviewing the type and severity of adverse events attributed to study procedures among each study group. See Section 8.0 for adverse event definitions and protocols.

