## 8.0 DATA AND SAFETY MONITORING

The Principal Investigator will meet with study staff on a monthly basis to review participant's adverse events, verify CTCAE grade, and provide attribution, and to review response data.

This study will employ a Data and Safety Monitoring Plan (DSM; see Appendix A) to outline how participant safety and confidentiality will be managed throughout the study. The PI and co-investigators have clinical licensure (RN or MD) and will review quarterly the following study data provided by the research team:

- Number of participants
- List of adverse event and responses that have occurred in the specified time frame
- Cumulative table of adverse events by type and grade, including deaths as outlined in the protocol-specific DSM
- Premature terminations of the intervention and other safety issues

At each review, the PI and co-I's will determine whether:

- The trial should continue as originally designed
- The trial should be changed
- The trial should be terminated
- Outcome results should be released prior to the reporting of the study results

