## 10.0 STATISTICAL CONSIDERATIONS

For objective 1, we will measure the feasibility of our intervention by calculating recruitment rates (% participants enrolled of those approached), enrollment rate (% enrolled of those eligible), lost to follow-up (% who dropped out of those enrolled), intervention discontinuation rate (% of intervention participants who permanently stop the intervention for any reason by Week 24), intervention attendance (% exercise sessions attended), relative dose intensity (% completed sessions), and compliance (based on accelerometry data, self-report of exercise via questionnaires). A benchmark to determine feasibility includes <40% loss to follow-up.

In objective 2, we will start with an analysis of the safety endpoints by calculating the number and percent of adverse events that occurred during the intervention and during the waitlist control period. This analysis will be stratified by the severity of the adverse events, the seriousness of the adverse events, and by the attribution of the adverse events.

The results from above analyses (for Study Aim 1) will be a primary consideration to inform the feasibility and safety of launching a larger scale intervention from the pilot intervention. If both these sets of data provide indications that the study is feasible and safe, then the exploration of additional intervention outcomes will take place. These data will be presented in a manuscript to describe the potential for this intervention. The following analyses will explore additional intervention outcomes to inform the intervention's potential to have an impact on CRF, functional capacity, physiologic changes, and PRO in a larger scale intervention.

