### COLLECTION AND REPORTING OF SAEs AND AEs

For this study, the following standard AE definitions are used:

**Adverse event:** Any unfavorable and unintended sign (including an abnormal laboratory finding), symptom or disease temporally associated with the use of a medical treatment or intervention procedure, regardless of whether it is considered related to the medical treatment or intervention procedure.

**Serious Adverse Event:** Any AE that results in any of the following outcomes:

- Death
- Life-threatening
- Event requiring inpatient hospitalization or prolongation of existing hospitalization
- Persistent or significant disability/incapacity

AEs are graded according to the following scale:

**Mild:** An experience that is transient & requires no special treatment or intervention. The experience does not generally interfere with usual daily activities. This includes transient laboratory test alterations. A mild AE typically corresponds to a 1 on the NCI Common Terminology Criteria for Adverse Events (CTCAE).

**Moderate:** An experience that is alleviated with simple therapeutic treatments. The experience impacts usual daily activities. Includes laboratory test alterations indicating injury, but without long-term risk. A moderate AE corresponds to a 2 on the CTCAE.

**Severe:** An experience that requires therapeutic intervention. The experience interrupts usual daily activities. If hospitalization (or prolongation of hospitalization) is required for treatment it becomes an SAE. A severe AE corresponds to a 3 on the CTCAE.

The study uses the following AE attribution scale:

**Not related:** The AE is clearly not related to the study procedures (i.e., another cause of the event is most plausible and/or a clinically plausible temporal sequence is inconsistent with the onset of the event).

**Possibly related:** An event that follows a reasonable temporal sequence from the initiation of study procedures, but that could readily have been produced by a number of other factors.

**Related:** The AE is clearly related to the study procedures.

AEs are identified by participant self-report at each study follow up assessments (12-, 24-, 36- and 48-weeks). Participants will be asked about medical or mental health events that have happened since the previous assessment visit. AEs may also be identified during supervised (in-person or remote) exercise sessions, with an event either occurring or being reported during such sessions.

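### The only by-group review of adverse event type is limited to events attributed to study procedures, and that attribution can differ by arm; tabulate type by arm for all events

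*Combined protocol and SAP*

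**What the plan says.** The safety endpoint in Section 4.2.2 (Intervention Safety) has two parts. The first is "reviewing and quantifying the number of adverse events (mild, moderate, or severe), serious adverse events", with no condition on cause. The second is "reviewing the type and severity of adverse events attributed to study procedures among each study group".

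The rest of the plan treats attribution as follows:

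- **Collection (Section 2.4).** "All adverse events, regardless of attribution to study procedures, will be collected and recorded".
- **Analysis (Section 10.0, objective 2).** The analysis starts by "calculating the number and percent of adverse events that occurred during the intervention and during the waitlist control period", and is "stratified by the severity of the adverse events, the seriousness of the adverse events, and by the attribution of the adverse events". Attribution is one way of splitting the events and does not decide which events enter.
- **Midpoint look (Appendix A, Data Analysis Plans).** Chi-square tests compare serious and other adverse events between intervention and control participants. Attribution enters only the later discussion about stopping.
- **Who attributes (Sections 7.1 and 8.0).** Section 7.1 rests attribution on the principal investigator's opinion. The monthly meeting in Section 8.0 is where that person and staff "verify CTCAE grade, and provide attribution".
- **What controls undergo (Sections 4.1, 4.3.5 and 6.2).** They have the same CPET, MRI, walk test and 1-RM schedule as exercisers, and no exercise sessions during the 24 weeks.

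**The concern.** Safety in intervention versus control is part of Aim 2. Section 10.0 makes the feasibility and safety results the gate to the exploratory outcomes and an input to the larger trial. Readers will want to know what kinds of events exercise produced beyond those seen without it. The randomised control arm can answer that without any causal judgement on individual events, provided event type is tabulated by arm for every event.

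The plan instead restricts its by-group look at type to events judged to stem from study procedures. Exercisers train about three times a week in addition to the shared assessments; controls have the assessments only. The same complaint arising in mid-trial has an obvious candidate cause in one arm and usually none in the other. A by-group display of attributed events then partly reflects the attribution step and not only the harm.

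**Working it through.** **Step 1. Which event features are tabulated by arm, and for which events?**

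| Source | Feature | Events included | By arm? |
|---|---|---|---|
| 4.2.2, first part | Number by grade; serious events | All | Not stated within this part |
| 4.2.2, second part | Type and severity | Attributed only | Yes |
| 10.0, objective 2 | Number and percent, by severity, seriousness and attribution | All | Yes |
| 8.0, quarterly review | Type and grade, cumulative | All | No arm split stated |
| Appendix A, midpoint | Overall proportions of serious and other events | All | Yes |

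Severity and seriousness have an all-event comparison by arm. Type does not, and neither does type crossed with severity.

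**Step 2. Can attribution differ by arm for similar events?** Three features of the text allow it.

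- Exposure differs: controls have no training sessions (Section 6.2).
- The Appendix A category of possible relation covers "An event that follows a reasonable temporal sequence from the initiation of study procedures" that could readily have had other causes. Someone training several times a week meets the timing condition more easily than a control between visits. Appendix A also ties its list of expected events, including fatigue and muscle soreness, to the exercise intervention.
- Masking is described only for MRI reading (Section 4.2.3). That the investigator knows the arm is an inference, but a reasonable one: Appendix A gives this person access to study data at all times and a role in deciding on return to exercise after moderate or severe events.

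The standard is also not uniform. Section 7.1 asks whether procedures were more likely than not the cause; Appendix A accepts a lower bar for possible relation. The set of attributed events depends on which is applied.

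**Step 3. Illustration of size.** The plan has no figure to reproduce: it gives no event rate, attribution rate or safety threshold. From the documents, 30 women split 2:1 gives 20 intervention and 10 control. Everything else here is assumed:

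- p = probability that a woman has an event of the kind in question, equal in both arms (no true effect);
- qI and qC = probability that such an event is attributed in the intervention and control arm.

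All-event risk difference = p − p = 0. Attributed-event risk difference = p × (qI − qC).

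Example with p = 0.4, qI = 0.5, qC = 0.1:

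- all events: 20 × 0.4 = 8 of 20 versus 10 × 0.4 = 4 of 10, difference 0;
- attributed events: 20 × 0.4 × 0.5 = 4.0 versus 10 × 0.4 × 0.1 = 0.4, so 0.20 − 0.04 = 0.16.

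| p | qI 0.5, qC 0.5 | qI 0.5, qC 0.1 | qI 0.8, qC 0.1 |
|---|---|---|---|
| 0.2 | 0 | 0.08 | 0.14 |
| 0.4 | 0 | 0.16 | 0.28 |
| 0.6 | 0 | 0.24 | 0.42 |

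The bias depends entirely on the gap between qI and qC, about which the documents say nothing. The zero for all events further assumes that events are detected equally well in both arms.

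**The case against.** The strongest reply is that the plan already has the unbiased counts. All events are recorded whatever their cause, all are counted by grade, and Section 10.0 and the midpoint test compare all events between groups. This stands, and it rules out several stronger readings that a reader might infer:

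- **That severity is compared only on attributed events.** It is not. The first part of the endpoint has no attribution condition, and in Section 10.0 attribution is a stratifier.
- **That the same event counts in an exerciser and not in a control.** It enters both arms' totals. It can drop out only of the attributed-only review.
- **That controls have nothing to attribute events to.** The criterion is study procedures, which include CPET, 1-RM, the walk test and MRI in both arms. Section 2.4 says CPET may cause fatigue and discomfort. Appendix A reserves its unrelated category for events clearly not caused by procedures, so no rule forces a control's complaint into it.
- **That a large bias has been shown.** Any figure rests on assumed rates, and setting control attribution to zero is an extreme choice.

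It can also be said that reviewing events in each group is description and not comparison. That reading is open, but the text does not say that attributed events will not be set side by side, and Aim 2 invites exactly that.

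Finally, all-event counts are not free of bias either. Appendix A allows events to be picked up at supervised exercise sessions, which controls do not attend. This is a fair limit on the remedy. It affects attributed counts as well, so it is no reason to prefer them.

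What the reply does not meet is event type: no section promises an all-event table of type by arm.

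**Conclusion.** The point holds in a narrow form. The by-group review of event type, and of type with severity, is confined to attributed events. Attribution is an investigator judgement with no stated masking, in arms that differ in exercise exposure, so that component is open to differential attribution. The likely direction is more attributed events in exercisers. The size is unknown; the 8 to 42 point range above holds only under the assumed rates and shrinks to zero if attribution is even. The planned all-event comparisons of severity and seriousness do not share this restriction. The importance is minor: this is a 30-woman pilot with no safety threshold, and the data needed for the better table will already be in hand.

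**What to change.** In Section 4.2.2 and Section 10.0:

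- State that adverse event type and severity will be tabulated by arm for all events, regardless of attribution.
- Keep attributed events as a supplementary description within each arm, and say that they are not used as a comparison between the exercise and waitlist arms.
- Say whether attribution is made with knowledge of the arm, and which attribution standard (Section 7.1 or Appendix A) defines the supplementary table.
- Record as a limitation that all-event counts may still differ by arm because supervised sessions give exercisers an extra route of detection.

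The cost is a few sentences of wording and one table; no new data are needed. The drawback is that an all-event table of type holds more unrelated events and is noisier.
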